6.5.9 Day 85/Early Treatment Discontinuation Visit

The following procedures and evaluations will be performed at the clinic on Day 85 or within 7 days of the last dose of study drug for subjects who discontinue study drug treatment early.

At this visit, the following procedures and assessments are to be performed:

- Cough severity VAS
- PGIC
- LCQ
- Vital signs
- Weight
- Collect Day 84 cough monitor
- Complete physical exam
- ECG (12 lead)
- Laboratory tests
 - Reproductive endocrine labs for females under 55 years of age at time of consent
 - Endocrine
 - Hematology
 - Chemistry
 - Urinalysis
 - Urine pregnancy test for females of childbearing potential
 - Urine drug screen
- Contact IWRS to register Day 85 end of treatment visit
- Review IVRS/IWRS Days 57–84 dosing diary entries
- The following will be completed by the Investigator (MD or DO):

- CGIC
- Study drug - collect/performance accountability for Days 57–84 bottles (**early treatment discontinuation visit only**)
- Record all AEs
- Record all concomitant medication use
- Schedule Day 112 visit at clinic or at subject's home
- Schedule Day 113 visit at clinic

6.5.10 *Day 112 Follow-up Visit*

Subjects will return to the clinic or be visited by a mobile research nurse on Day 112 (± 3 days) for the following procedures and evaluations:

- Cough severity VAS
- Record all AEs
- Record all concomitant medication use
- Attach and activate cough monitor
 - Cough monitor will be collected the following day by a courier service and delivered to the clinic
- Contact IWRS to register the Day 112 Follow-up visit
- Remind subject about Day 113 visit at clinic

6.5.11 *Day 113 Follow-up Visit*

Subjects will return to the clinic on Day 113 for the following procedures and evaluations:

- Vital signs
- Collect Day 112 cough monitor
- Cough severity VAS
- LCQ
- Contact IWRS to register the Day 113 Follow-up visit
- Complete physical exam
- ECG (12-lead)

- Laboratory tests
 - Reproductive endocrine labs for females under 55 years of age at time of consent
 - Endocrine
 - Hematology
 - Chemistry
 - Urinalysis
 - Urine pregnancy test for females of childbearing potential
 - Urine drug screen
- Record all AEs
- Record all concomitant medication use

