- Proportion of subjects with $\geq 30\%$ reduction in awake objective cough frequency per hour at Week 12
- Change from baseline in Cough Severity Visual Analog Scale (VAS) at Week 12

Other Secondary

- Change from baseline in 24-hour objective cough frequency after 4 and 8 weeks (Day 28 and 56) of treatment
- Change from baseline in awake objective cough frequency after 4 and 8 weeks (Day 28 and 56) of treatment
- Change from baseline in 24-hour objective cough frequency at the Follow-Up visit (Day 112)
- Change from baseline in sleep objective cough frequency after 4, 8 and 12 weeks (Day 28, 56 and 84) of treatment
- Change from Baseline in Cough Severity Visual Analog Scale (VAS) at Weeks 4 and 8
- Change from Baseline in Leicester Cough Questionnaire (LCQ) individual Domain and Total scores
- Patient's Global Impression of Change (PGIC)
- Clinician's Global Impression of Change (CGIC)

Statistical approaches for analysis of the secondary endpoints will be detailed in the SAP. The continuous secondary efficacy endpoints will be analyzed using the same MMRM model as used for the primary efficacy analysis.

The categorical secondary efficacy endpoints will be analyzed using the stratified Miettinen and Nurminen (M&N) method, adjusting for gender and country.

Table 2 Analysis Strategy for Primary and Key Secondary Efficacy Endpoints

Endpoint	Statistical Method	Analysis Population	Missing Data Approach
Primary Efficacy Endpoint			
Change from baseline in 24-hour objective cough frequency after 12 weeks (Day 84) of treatment	MMRM	FAS	Observed data only
			Reference-based imputation & Tipping-point approach
Key Secondary Efficacy Endpoints			
Change from baseline in awake objective cough frequency after 12 weeks (Day 84) of treatment	MMRM	FAS	Observed data only
Proportion of participants with $\geq 30\%$ reduction in 24-hour objective cough frequency after 12 weeks (Day 84) of treatment	Stratified Miettinen and Nurminen (M&N)	FAS	Observed data only
Proportion of participants with $\geq 30\%$ reduction in awake objective cough frequency after 12 weeks (Day 84) of treatment	Stratified Miettinen and Nurminen (M&N)	FAS	Observed data only
Change from baseline in VAS after 12 weeks (Day 84) of treatment	MMRM	FAS	Observed data only

MMRM = Mixed Model Repeated Measures; GLMM= Generalized Linear Mixed Model; VAS = Visual Analogue Scales; FAS = Full Analysis set;

8.9.4 *Multiplicity Adjustment*

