## 6.0 ANALYSIS SETS

### 6.1 Full Analysis Set (FAS)

All randomized subjects who have taken at least one dose of study medication and provided at least one baseline and at least one post-baseline primary endpoint observation during the treatment period. Participants will be analyzed according to the treatment group to which they are randomized.

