### 8.1 General Analysis Considerations

For continuous variables, descriptive statistics will include the number of subjects reflected in the calculation (n), mean, standard deviation, median, minimum and maximum. Categorical variables will be summarized using frequency counts and percentages. Treatment differences in response rates (e.g., proportion of cough frequency responders) will be estimated using the stratified Miettinen and Nurminen (M&N) method (stratified by country and sex). Treatment differences in continuous data collected over multiple study visits (e.g., changes from baseline in awake cough frequency) will be assessed using the MMRM model with treatment, visit (nominal time point), country, sex, and the visit by treatment interaction as fixed effects, and baseline value as covariates.

Individual subject data obtained from the electronic case report forms (eCRFs), central laboratory, cough monitoring data, diary data, and any derived data will be presented by subject in data listings to facilitate the investigation of tabulated values and to allow for the clinical review. In general, all tables will be presented by treatment group and listings will be displayed by sorted unique subject identifier and treatment group. A subject identification number is defined as a 3-digit site number followed by a 3-digit sequentially assigned subject id (xxx-xxx). The treatment group in the listings will be based on the planned treatment(s) as allocated by the randomization scheme.

All p-values will be rounded to 4 decimal places. If a p-value is less than 0.0001 it will be displayed as “< 0.0001”, a p-value rounding to 1 will be displayed as “> 0.9999”. Unless otherwise specified all summaries will be performed by treatment group, all efficacy analyses will be based upon the FAS and all safety analyses will be based upon the Safety Analysis Set. Demographic and baseline characteristic analyses will be based upon the FAS, Safety All Randomized Subjects. The safety and demographic tables will include a total column along with the treatment columns.

The analyses described in this plan are considered a priori, in that they have been defined prior to database lock. Any analyses not described herein performed subsequent to database lock will be considered post hoc and exploratory.

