### 9.6.2 Primary Endpoint

The primary endpoint of the study is the change from baseline in 24-hour objective cough frequency after 12 weeks (Day 84) of treatment.

Cough monitoring is conducted for Baseline (Study Day -1) and 24 hours after administration of the study drug on Days 28, 56, 84, and 112. An independent cough monitoring analysis center

will provide documentation of the time of each cough event over the 24-hour period, as well as the time when the subject goes to sleep and the time the subject awakens.

A negative result indicates a decrease in cough frequency, while a positive result indicates an increase in cough frequency. The Baseline cough frequency is derived from the cough monitoring performed at Baseline Visit (Study Day -1), and the post-dose cough frequency is derived from the cough monitoring performed on Days 28, 56, 84, and 112. Change from baseline and percent change in 24-hour objective cough frequency will be calculated for each visit. For descriptive summary only, the percent change from baseline will be capped at 200% for any value > 200%.

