#### **9.6.5 Sensitivity Analysis**

The primary analyses (MMRM) for assessing 24-hr cough frequency and awake cough frequency are valid if the missing data are missing at random (MAR), meaning that the probability of a value being missing, conditional on the observed data and factors in the statistical model, is random and not dependent on the unknown value of the missing data point. Therefore, two sensitivity analyses under missingness not at random (MNAR) will be conducted for 24-hr cough frequency and awake cough frequency to evaluate the robustness of efficacy results and the effect of missing data.

Sensitivity analysis using a copy-reference multiple-imputation method will be performed to assess the robustness of the primary analysis based on MMRM. In this sensitivity analysis, intermittent missing values will be imputed using the Markov Chain Monte Carlo (MCMC) methodology which assumes a multivariate normal distribution over all variables included in the imputation model. This imputation will be done by treatment group, using MI procedure in SAS 9.4. The variables to be used in the imputation are treatment, corresponding baseline values, and values observed at all double-blind visits (Days 28, 56, and 84). Then all the monotone missing values will be multiply-imputed using the imputation model built from the control group, i.e., assuming the missing data in the treatment group will have a profile that equals the profile of the control group for all time points (i.e., a copy-reference imputation). The missing data imputation will be implemented using PROC MI in SAS 9.4 with the MNAR statement. Once the competed

data sets are formed, the same MMRM analysis model as specified for the primary analysis will be applied to each completed set and the inference drawn using Rubin's combination rules (SAS proc MIANALYZE). While the results will be combined using SAS PROC MIANALYZE, it is known that this approach may produce an inflated variance estimate for the treatment comparison. To get a correct variance, a pattern mixture model approximation method will also be used. Results from both the MIANALYZE and the pattern mixture model approximation will be presented as sensitivity analyses. A sample of SAS code for sensitivity analysis using the copy-reference MI method is provided in Appendix A.

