**A sample of the SAS code for sensitivity analysis using the copy-reference MI method is provided as below:**

```
/*Generate transpose of adcf - wide format before Step 1*/
/*----- Generates 10 imputed data sets based on original (non-transformed)
data-----*/
/*Step 1: Achieve Monotone Missing Data Pattern */
PROC MI DATA=&DATA SEED=14823 NIMPUTE=10 OUT=MONO;
  /* Use numeric TRT01PN */
  VAR BASE AVAL1 AVAL2 AVAL3; /*Refer to AVAL at Visits 5, 6, and 7*/
  MCMC IMPUTE=MONOTONE NBITER=5000 NITER =5000;
  BY TRT01PN;
run;

/*Step 2: Achieve Control-Based Copy-Reference Imputation */

PROC MI DATA=MONO SEED=14823 NIMPUTE=1 OUT=OUTM1;
  CLASS TRT01PN;
  By _IMPUTATION_;
  VAR TRT01PN BASE AVAL1 AVAL2 AVAL3;
  MONOTONE REG (AVAL2 AVAL3);
  MNAR MODEL (AVAL1 AVAL2 AVAL3/ MODELOBS = (TRT01PN = '0'));
  /*Control=Placebo*/
RUN;
PROC SORT DATA =OUTM1; BY _IMPUTATION_ TRT01PN USUBJID LBASE; RUN;
/*Generate transpose of OUTM1 - skinny format before Step 3*/

/*Step 3: Run MMRM Analysis on Imputed Data */

PROC MIXED DATA=OUTM1 METHOD=REML;
  BY _IMPUTATION_;
  CLASS TRT01PN USUBJID AVISITN COUNTRY SEX;
```

```

MODEL LCHG = TRT01PN AVISITN COUNTRY SEX TRT01PN*AVISITN LBASE / DDFM=KR;
/*LCHG AND LBASE ARE BASED ON THE LOG-TRANSFORMED COUGH FREQUENCY*/
REPEATED / SUBJECT=USUBJID (TRT01PN) TYPE=UN;
LSMEANS TRT01PN*AVISITN / CL DIFF PDIFF;
  ESTIMATE 'TRT S - P ON DAY 28' TRT01PN -1 1
            TRT01PN*AVISITN -1 0 0 1 / CL LOWER LOWERTAILED;
  ESTIMATE 'TRT S - P ON DAY 56' TRT01PN -1 1
            TRT01PN*AVISITN 0 -1 0 0 1 / CL LOWER LOWERTAILED;
  ESTIMATE 'TRT S - P ON DAY 84' TRT01PN -1 1
            TRT01PN*AVISITN 0 0 -1 0 0 1 / CL LOWER LOWERTAILED;
ODS OUTPUT PARAMETERESTIMATES=PESTIMATES;
RUN;
```

```

/*Step 4: Combining estimates from each imputed data set */
/*First, sort the data of estimates by visit (variable "LABEL") */
PROC MIANALYZE DATA=PESTIMATES;
  MODELEFFECTS ESTIMATE;
  STDERR STDERR;
  BY LABEL;
  ODS OUTPUT PARAMETERESTIMATES= MIPARM;
RUN;
```

A sample of the SAS code for sensitivity analysis using the tipping-point approach is provided as below:

```

/*-----*/
/*--- Performs multiple imputation analysis ---*/
/*--- for specified shift parameters: ---*/
/*--- data= input data set ---*/
/*--- smin= min shift parameter ---*/
/*--- smax= max shift parameter ---*/
/*--- sinc= increment of the shift parameter ---*/
/*--- outparms= output parameters ---*/
/*-----*/

%MACRO MIPARMS( DATA=, SMIN=, SMAX=, SINC=, OUTPARMS=);

DATA &OUTPARMS;

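### Both missing-not-at-random sensitivity analyses run on the FAS, so dosed subjects who stop before their Day 28 recording are never imputed and the results look somewhat more robust than they should

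*SAP*

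**What the plan says.** **Analysis set.** Protocol 8.4 and SAP 6.1 define the FAS in the same way: randomised, at least one dose, and "provided at least one baseline and at least one post-baseline primary endpoint observation during the treatment period". Under SAP 8.1, unless otherwise specified, "all efficacy analyses will be based upon the FAS and all safety analyses will be based upon the Safety Analysis Set". In Protocol Table 2 the entry "Reference-based imputation & Tipping-point approach" stands under the primary endpoint, whose population is the FAS.

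**Sensitivity analyses.** SAP 9.6.5 plans two analyses under missingness not at random, "to evaluate the robustness of efficacy results and the effect of missing data". Intermittent gaps are filled first. "Then all the monotone missing values will be multiply-imputed using the imputation model built from the control group". The tipping-point analysis shifts imputed values in the active arm. Neither description names a set other than the FAS.

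**Recordings.** SAP 9.6.2 gives the schedule: "Cough monitoring is conducted for Baseline (Study Day -1) and 24 hours after administration of the study drug on Days 28, 56, 84, and 112". Protocol 6.5.6 allows 3 days either side of Day 28. The early treatment discontinuation visit attaches no monitor; its only monitor item is "Collect Day 84 cough monitor" (Protocol 6.5.9 and Appendix A, Table 3). SAP Appendix B, note r, waives the Day 112 recording after early discontinuation. SAP 7.3 classes recordings after the last dose as follow-up.

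**Sample code.** In SAP Appendix A the copy-reference step contains "MONOTONE REG (AVAL2 AVAL3", which covers Day 56 and Day 84. The MNAR line below it also names AVAL1 (Day 28), and the tipping-point code shifts AVAL1 too.

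**The concern.** The two analyses exist to show what happens if missing outcomes do not follow the missing-at-random assumption. Before either begins, the FAS rule removes dosed subjects with no on-treatment post-baseline recording. That removal depends on events after randomisation and could differ by arm: Protocol 5.6, for example, ends study drug for a Grade 2 or higher treatment-emergent event judged likely related.

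The direction follows from the methods. Copy-reference imputation of further active-arm subjects pulls the estimate toward no effect. In the tipping-point analysis the shift acts only on imputed active values, so with fewer of them a larger shift is needed to overturn the result. Leaving out the earliest dropouts therefore makes both analyses look more reassuring. No analysis of all dosed or all randomised subjects is planned as a counterweight.

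**Working it through.** **1. The plan's own sample size** (Protocol 8.1, SAP 8.2: ratio 0.75, CV 0.64, one-sided 0.05, 90% power, 15% dropout)
- Log effect d = |ln 0.75| = 0.2877.
- Log SD = sqrt(ln(1 + 0.64²)) = 0.5859.
- The two-sample t-test needs 71.7, so 72 per arm. 72/0.85 = 84.7, so 85 per arm and 170 in total. The stated figure reproduces exactly.

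**2. Who is left out**
Let f be the share of the 15% dropout that occurs before the first recording. The documents do not give f, so it is varied as an assumption. The excluded fraction is e = 0.15f, and 85e subjects per arm are lost:
- f = 0.25: e = 0.0375, 3.2 per arm
- f = 0.5: e = 0.075, 6.4 per arm
- f = 1: e = 0.15, 12.75 per arm (upper bound)

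**3. Copy-reference estimate**
Later dropouts have a Day 28 value, and the imputation conditions on it, so they keep a share r of the effect (r = correlation between visits, assumed). Subjects with baseline only keep none. With late fraction L = 0.15 − e:
- FAS: d × [1 − (L/(1 − e)) × (1 − r)]
- All dosed: d × [1 − L(1 − r) − e]

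For r = 0.6 and f = 0.5: L/(1 − e) = 0.075/0.925 = 0.0811. The FAS ratio is exp(−0.2877 × 0.9676) = 0.757, and the all-dosed ratio is exp(−0.2877 × 0.895) = 0.773.

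A simulation of copy-reference imputation (1,500 runs, 85 per arm, 10 imputations, Rubin's rules, r = 0.6, equal dropout in both arms, Day 28 and Day 84 only) gave:

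| f | Ratio, FAS | Ratio, all dosed | Power, FAS | Power, all dosed |
|---|---|---|---|---|
| 0.25 | 0.757 | 0.765 | 90% | 89% |
| 0.5 | 0.756 | 0.772 | 90% | 87% |
| 1 | 0.750 | 0.783 | 90% | 84% |

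The simulation standard error of each power is about sqrt(0.9 × 0.1/1500) = 0.8 points. With r from 0.5 to 0.8, the formulas give gaps between the sets of about 0.008 at f = 0.25 and 0.016 at f = 0.5, in line with the simulation.

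**4. Tipping shift, log scale, observed effect equal to plan**
- SE = 0.5859 × sqrt(2/72.25) = 0.0975, held equal for both sets.
- Margin before significance is lost: 0.2877 − 1.645 × 0.0975 = 0.1273.
- All dosed: 0.1273/0.15 = 0.85, whatever f is.
- FAS, f = 0.25: imputed fraction 0.1125/0.9625 = 0.1169, shift 1.09, inflation 0.15/0.1169 = 1.28.
- FAS, f = 0.5: imputed fraction 0.0811, shift 1.57, inflation 0.15/0.0811 = 1.85.
- FAS, f = 1: nothing is left to impute, so there is no tipping point.

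**5. Treatment codes in the sample program**
SAP Appendix A sets TRT01PN to 1 for placebo and 2 for serlopitant. The copy-reference code builds its reference model on code 0, which matches neither arm. The tipping-point code shifts code 1, which is placebo. A wider analysis set would not correct this.

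**The case against.** **The rule is pre-specified and the same in both documents.** That is right: this is a design weakness, not a contradiction. No primary or key secondary test changes, because subjects with no post-baseline value add almost nothing to the MMRM. The losses will also be partly visible, since disposition by arm and reason (SAP 9.1) and discontinuations due to adverse events (SAP 9.7.1) are tabulated. Those tables show how many left, but not what their outcomes could do to the estimate.

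**The effect is modest.** This also stands. The ratio moves by 0.01 to 0.02 and power by 1 to 3 points for f of 0.25 to 0.5. The power loss appears under Rubin's variance. SAP 9.6.5 also reports a pattern-mixture variance, under which estimate and standard error shrink together. At f = 1, for example, both are multiplied by 0.85, so the test changes little although the estimate still moves. The tipping shift is affected either way.

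**Stronger readings that the documents do not support.**
- A reader might take the regression statement in the sample code as proof that baseline-only subjects cannot be imputed. The code is mixed on Day 28, because its MNAR statements name AVAL1, and it is labelled as a sample. The case rests on the FAS rule.
- A reader might infer that everyone who stops in the first four weeks is lost. A subject recorded on Day 25 who then stops is in the FAS.
- A reader might remove the whole effect from every dropout. That ignores the visits on which the imputation conditions, and overstates the dilution on the FAS.
- A reader might assume that these are the most informative dropouts. Nothing in the documents shows it.

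**Conclusion.** The point holds on structure. Dosed subjects who stop before their Day 28 recording have no scheduled route into the FAS and are outside both analyses meant to examine missing data. The bias in those analyses is toward apparent robustness.

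The size is an assumption-based range. With a quarter to a half of the 15% dropout before the first recording, the effect on the copy-reference result is small and the effect on the tipping shift is more noticeable. It fades if almost nobody leaves that early and grows if most do. The figures assume equal dropout in both arms, the visit correlations shown, and an observed effect equal to the planned one. The shifts on the log scale are illustrative, because SAP 9.6.5 imputes before log-transforming and its example shifts run from 0 to 100 on the original scale. The primary analysis is not called into question. The change is nevertheless worth making before database lock.

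**What to change.** 1. Keep the FAS for the primary MMRM.
2. In SAP 9.6.5, state that both sensitivity analyses use all randomised, dosed subjects with a baseline recording.
3. In SAP Appendix A, add AVAL1 to the MONOTONE REG list so that Day 28, 56 and 84 are all explicitly imputed.
4. Align the treatment codes with the definition in the same appendix: MODELOBS should select placebo (TRT01PN = 1), and the shift should apply to serlopitant (TRT01PN = 2).
5. Report the number excluded from the FAS by arm and reason.

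The cost is some SAP wording and a few lines of code. No new data are needed, and Protocol 8.9.2.1 already leaves the technical details of these analyses to the SAP. Because Protocol Table 2 lists the FAS for these analyses, the SAP should record the wider set as a deliberate change. The downside is a slightly less favourable sensitivity result.

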### 6.2 Safety Analysis Set

The safety analysis set will consist of all subjects randomized who receive at least one dose of study medication. Subjects will be classified based upon the treatment received.

### 6.3 PK Analysis Set

The PK analysis set will consist of all subjects who receive  $\geq 1$  dose of serlopitant and who have at least 1 post-dose PK blood sample available for analysis.

## 7.0 DEFINITION OF VARIABLES

### 7.1 Baseline

For purposes of assessing changes in vital signs, physical examination results, 12-lead ECG results and clinical laboratory values, baseline refers to the study as a whole and is defined as the last observation prior to the first study treatment. For all efficacy variables, baseline refers to the observation collected at Baseline visit (Study Day -1).

### 7.2 Study Day

Study Day 1 is the date of first study medication. Study Day relative to Study Day 1 will appear in the listings where applicable.

If the date of event is on or after the 1st study medication date then

$$\text{Study Day} = \text{date of event} - \text{date of 1}^{\text{st}} \text{ study medication} + 1$$

If the date of event is prior to the first study medication then:

$$\text{Study Day} = \text{date of event} - \text{date of 1}^{\text{st}} \text{ study medication}$$

### 7.3 Analysis Windows

The analysis windows used to report cough frequency endpoints are outlined in Table . If more than one assessment is available within the range the assessment closest to the target day is reported for the analyses window. If two observations exist with the same distance to the target day, the first observation is used.

